8.2 Objectives

8.2.1 Primary Objective

- To assess the safety of PEP-CMV vaccination in combination with adjuvant TMZ.
- To determine the TMZ regimen that produces the highest number of T cells that specifically secrete IFN γ by ELISPOT in response to PEP-CMV component A.

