Patients who are dependent on steroid supplements above immune suppressive levels (4 mg daily) at time of vaccination or who are unable to tolerate TMZ will be withdrawn from the study before vaccination therapy (see Section 10.2). In order to meet the goal of obtaining 26 evaluable patients who received Component A only (13 patients per arm) for the primary outcomes, up to 70 patients may be consented on the main informed consent.

For both study arms, the initial Duke visit will be within 3 ± 1 weeks after completion of standard of care radiation. For Arm 1, the initial cycle of TMZ will begin as soon as possible after randomization at a standard targeted dose of 150-200mg/m²/d for 5 days. For Arm 2, the initial cycle of TMZ will begin, as soon as possible after randomization at the dose-intensified dose of 75-100 mg/m²/d for 21 days. All patients will have immune monitoring blood drawn and then receive a tetanus pre-conditioning injection (Td 1 flocculation unit, Lf, in 0.4 mLs of saline) in the RIGHT groin (as described below) on day 22 (+1 day). Additional safety measures were implemented in this study during the latter half of 2019 and the beginning of 2020, resulting from safety events on study. Patients will receive their 1st vaccine in the Oncology Treatment Center (OTC) and will receive a normal saline bolus

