11.5.5 Adverse Event Reporting and Documentation

An “Adverse Event” will be defined as any adverse change from the subject’s pre-treatment baseline condition (which is based on the physical and neurologic assessment done at the SOC clinic visit prior to initiation of post-radiation chemotherapy and vaccine therapy), including any clinical or laboratory test abnormality that occurs during the course of research **after** vaccine treatment has started. Adverse events will be categorized and graded in accordance with the NCI CTCAE (Version 4.03).

A “Serious Adverse Event” will be defined as an undesirable sign, symptom or medical condition which: 1) is fatal or life threatening; 2) requires inpatient hospitalization or a prolongation of existing hospitalization; 3) results in persistent or significant disability/incapacity; 4) constitutes a congenital anomaly or a birth defect and/or; 5) is medically significant such that it may jeopardize the subject, and may require medical or surgical intervention to prevent one of the outcomes listed above.

A summary of all adverse events (not just those considered related to the DC vaccine) will be kept which will categorize the event by organ system, relationship to treatment, its grade of severity, and resolution. The PI will periodically review the collective adverse events with the intention of identifying any trends or patterns in toxicity. If any such trends are identified, depending on their severity and frequency, a protocol amendment will be considered.

All adverse events which are serious and unexpected (as defined by 21CRF312.32[a]) should be reported immediately to [name] ([contact]) or his designee [contact]). Fatal or life-threatening, unexpected adverse events that are related or possibly related to the research will be reported to the FDA by telephone, facsimile, or in writing as soon as possible, but no later than 7 calendar days after first knowledge by the sponsor followed by as complete a report as possible within 8 additional calendar days. Serious, unexpected adverse events that are related or possibly related to the research and are not fatal or life-threatening will be reported to the FDA by telephone, facsimile, or in writing as soon as possible, but no later than 15 calendar days after first knowledge by the sponsor.

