11.8 Definition of Evaluable Subjects, On Study, and End of Study

Subjects evaluable for the analysis of the primary endpoints will include all randomized patients who undergo immune monitoring post vaccine #3, prior to 2nd vaccine/TMZ cycle. Survival analyses will include all randomized patients evaluable for the primary outcome.

Safety analyses will include all patients who receive vaccine treatment.

Once the patient signs an ICF, that subject will be considered “on study”. Rationale for taking patient off protocol treatment (see Section 11.10.1 below) will be documented.

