12.3 Physical and Neurological Examination

Physical examinations are to be completed by the investigator or designated participating clinician. The minimum body systems to be examined for any abnormalities and symptoms include: general appearance; skin; lymphatic; head, eyes, ears, nose, throat; extremities; respiratory; cardiovascular; abdominal; musculoskeletal; neurological and genitourinary.

General neurological assessments are to be completed by the investigator or designated participating clinician. The assessment includes but is not limited to: a general

¹³ During vaccine 1: just prior to Component A, 1 and 2 hours after Component A (~20 mL, 1 EDTA lavender top tube and 1 serum red top tube at each blood draw). Just prior to vaccine 2 (1 EDTA lavender top tube, 1 serum red top tube, and 6 yellow ACD tubes). During vaccine 2: 1 and 2 hours after Component A (~20 mL, 1 EDTA lavender top tube and 1 serum red top tube at each blood draw). Just prior to vaccine 3 (9 yellow ACD tubes).

¹⁴ Prior to Td pre-conditioning (~90 mL, 9 yellow ACD tubes and 2 red serum tubes)

¹⁵ At the clinic visit 2 weeks after vaccine 3 [+3 days] (~90 mL, 9 yellow ACD tubes and 2 red serum tubes)

¹⁶ Prior to vaccines #4 and #6 (~90 mL, 9 yellow ACD tubes and 2 red serum tubes)

¹⁷ Immune monitoring blood and pathology testing performed at progression, if possible

¹⁸ Vital signs will be measured at all protocol-indicated visits before and approximately every 30 minutes after vaccination during the post-vaccine monitoring times described in Sections 11.4.2 and 12.6, until discharged from the clinic. Measurements to be reported include temperature in Celsius or Fahrenheit, pulse (beats per minute), respiratory rate (breaths per minute) and blood pressure.

¹⁹ MRI at prior to TMZ cycle 2 clinic visit (within 2 weeks +3 days after vaccine 3)

²⁰ MRI visits take place at the vaccine visit that coincides with the end of TMZ/vaccine cycles 1, 3, 5, 7, 9, 11 and then after every other vaccine visit during the post-TMZ period.

²¹ Pathology testing is performed per BTC standard of care practice and is obtained at the time of new patient evaluation

²² Adverse events and con meds will be collected throughout the study starting with the post-XRT/TMZ screening visit.

mental status examination (orientation, memory, attention/concentration, and language), assessment of cranial nerves, motor, coordination and gait, reflexes, and sensory evaluation.

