15.4 Analytic Methods

15.4.1 Primary Analyses

Safety: To assess the safety of PEP-CMV vaccination in combination with adjuvant TMZ, the percentage of patients with unacceptable toxicity will be estimated within each arm. All patients who received any PEP-CMV vaccine will be included in these safety analyses.

As described in Section 15.1, the vaccination treatment regimen has been modified over time due to safety issues. Hence, toxicity will be summarized for each period of study conduct as follows:

- Initial randomization period where patients were assigned to one of two TMZ regimens with both Component A and B. The 2 patients assigned to standard TMZ after randomization resumed who received both Component A and B will also be included in this summary.
- Safety Cohort Period in which all patients received standard TMZ with vaccine Component A and B
- Randomization period in which patients received at least one cycle of Component B prior to discontinuation
- Randomization period in which patients are assigned to one of two TMZ regimens and receive only vaccine Component A

Immunologic Response: The primary analysis will focus on patients who have follow-up immunologic monitoring after the 3rd vaccination and before initiation of the second TMZ/vaccine cycle. Such a patient is considered “evaluable” for the immunologic response primary analyses.

The Wilcoxon rank sum test will compare treatment groups with regard to the median peak number of T cells that secrete IFNy by ELISPOT in response to component A of PEP-CMV. Analyses will include only those patients who have an assessment of immune response after receiving 3 vaccinations.

Though the original vaccination included Component A and B, the primary immunologic analysis will focus on only those patients who received Component A alone. Additional exploratory analyses may include data from the few “evaluable” patients who received both vaccine Components A and B.

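### The adverse-event start date is contradictory, and cycle-1 temozolomide toxicity and pre-vaccine withdrawals appear in no by-arm safety result, although the primary objective names the combination

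*Combined protocol and SAP*

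**What the plan says.** The first primary objective (8.2.1) is "To assess the safety of PEP-CMV vaccination in combination with adjuvant TMZ". For its analysis, Section 15.4.1 states that "the percentage of patients with unacceptable toxicity will be estimated within each arm".

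Three sets of rules decide what reaches that result.

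- **Start of the adverse-event window.** Section 11.5.5 requires a change that "occurs during the course of research after vaccine treatment has started". The same sentence takes its baseline from the "SOC clinic visit prior to initiation of post-radiation chemotherapy and vaccine therapy". Table 3 footnote 22 says otherwise: "Adverse events and con meds will be collected throughout the study starting with the post-XRT/TMZ screening visit".
- **Safety population.** Section 11.8: "Safety analyses will include all patients who receive vaccine treatment". Section 15.4.1: "All patients who received any PEP-CMV vaccine will be included in these safety analyses". Section 11.5.4 tracks toxicity in the same vaccinated group.
- **Endpoint.** Section 11.5.4 and the synopsis define unacceptable toxicity as toxicity at least possibly related to the vaccine, with listed exceptions.

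On patients who fail TMZ, Section 11.1 says that those "who are unable to tolerate TMZ will be withdrawn from the study before vaccination therapy". The synopsis adds that they are replaced.

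**The concern.** The two randomised arms differ only in the TMZ regimen, and the whole first cycle of that regimen is given before the first vaccine. A reader who wants to know whether the combination is safe, arm by arm, would expect to see what happened in those weeks: cytopenias, dose changes, reactions to the Td booster or Td pre-conditioning, and patients who never reached vaccination.

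Whether events in that period count as adverse events depends on which of two conflicting passages is followed. Patients who leave during it are outside the safety set under either passage. Leaving for TMZ intolerance happens after randomisation and can depend on the assigned arm. One arm could therefore lose more patients before vaccine 1 without any specified by-arm safety result showing it. The ELISPOT comparison of the two regimens would then be read without that information beside it.

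**Working it through.** The plan gives no figure to reproduce here. The check concerns timing, definitions and a hypothetical range.

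**1. Timing.** Table 3 footnote 7 gives TMZ days as 1-5 (Arm 1) and 1-21 (Arm 2). Footnote 8 puts vaccine 1 on day 23 (+2 days). The synopsis windows allow day 22 at the earliest. Scheduled cycle-1 TMZ days before vaccine 1 are therefore 5 of 5 in Arm 1 and 21 of 21 in Arm 2. Of the blood draws at days 14, 21 and 28 (±2), the first two nominally precede vaccine 1; the day-21 draw may fall on day 23.

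**2. Planned cycle-1 dose** (Section 11.1 ranges).
- Arm 1: 5 × 150 = 750 to 5 × 200 = 1000 mg/m².
- Arm 2: 21 × 75 = 1575 to 21 × 100 = 2100 mg/m².
- Like for like: 1575/750 = 2.1 and 2100/1000 = 2.1.

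**3. Share of randomised TMZ.** MGMT-unmethylated patients enrolled after approval of v.20181218 receive one cycle only (11.1), so all of their randomised TMZ precedes vaccine 1. For patients who continue, cycles 2-12 fall after it.

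**4. The rules side by side.**

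| Case | 11.5.5 definition | Footnote 22 | Safety set | Primary percentage |
|---|---|---|---|---|
| Vaccinated; cycle-1 TMZ event resolved before vaccine 1 | not an adverse event | collected | in | not counted: precedes the vaccine |
| Withdrawn for TMZ intolerance before vaccine 1 | not an adverse event | collected | out | not counted |
| Vaccinated; event due only to TMZ in cycles 2-12 | adverse event | collected | in | not counted: not vaccine-related |
| Vaccinated; event at least possibly vaccine-related | adverse event | collected | in | counted if the 11.5.4 criteria are met |

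The last column shows that the vaccine-related endpoint alone keeps TMZ-only toxicity out of the primary percentage. The set decides whether the patient appears at all. The window decides whether the event is defined as an adverse event.

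**5. Hypothetical range.** The documents give no pre-vaccine withdrawal rate. Assume 13 vaccinated patients in an arm (the evaluable target, used as a convenient denominator), t of them with a counted event, and d further patients withdrawn for TMZ toxicity before vaccine 1. The vaccinated-only rate is t/13. A rate in all who started TMZ, with those withdrawals counted, is (t + d)/(13 + d).

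| d | t = 0: t/13 | t = 0: all starters | t = 2: t/13 | t = 2: all starters |
|---|---|---|---|---|
| 0 | 0% | 0% | 15.4% | 15.4% |
| 1 | 0% | 1/14 = 7.1% | 15.4% | 3/14 = 21.4% |
| 2 | 0% | 2/15 = 13.3% | 15.4% | 4/15 = 26.7% |
| 3 | 0% | 3/16 = 18.8% | 15.4% | 5/16 = 31.2% |
| 4 | 0% | 4/17 = 23.5% | 15.4% | 6/17 = 35.3% |

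If the set and window were widened but the endpoint stayed vaccine-related, the rate would fall instead: with t = 2 and d = 2, from 2/13 = 15.4% to 2/15 = 13.3%. Widening alone is therefore not a remedy.

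**The case against.** The strongest defence is that the safety question is about the vaccine. The hypothesis in Section 8.1 concerns PEP-CMV given during recovery from TMZ-induced lymphopenia, and a vaccinated set with a vaccine-related endpoint fits that question. This stands, and it is why the primary percentage should be kept.

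The plan also does not leave the period blank. Table 3 marks adverse-event collection as ongoing and schedules blood counts in cycle 1. Section 11.5.5 keeps a summary of events of every attribution. Section 11.8 requires the reason for leaving protocol treatment to be recorded. Section 11.10.3 keeps replaced patients' data in whatever analyses are appropriate. The raw information is therefore probably recoverable. But the 11.5.5 summary inherits the 11.5.5 definition and is not specified by arm, and the general wording of 11.10.3 does not override an explicit vaccinated-only set.

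A reader might infer that the window simply opens at the first vaccine. The documents do not settle that. They contradict each other, and a cytopenia still present after vaccine 1 might count as a change from the pre-chemotherapy baseline.

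A reader might also infer that the window and population rules are what remove TMZ toxicity from the primary percentage. The endpoint definition is the main reason.

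Finally, a difference between arms before vaccine 1 is plausible but not shown. Patients unable to tolerate TMZ are excluded at entry, and Table 1 provides for delay and reduction before discontinuation. The sustained Grade 3 lymphopenia reported for the 21-day regimen in Section 9.5 arose by cycle 3 (Figure 6 legend) or cycle 5 (text), not in cycle 1.

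**Conclusion.** The point holds in two parts. First, Section 11.5.5 and Table 3 footnote 22 give incompatible start dates for adverse events, and 11.5.5 is also out of step with its own baseline. Second, cycle-1 TMZ toxicity and withdrawals before vaccine 1 appear in no specified by-arm safety result, although the first primary objective names the combination and TMZ is the only randomised difference.

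The period affected covers all cycle-1 TMZ in both arms, and all randomised TMZ for MGMT-unmethylated patients enrolled after v.20181218. The numerical effect is unknown. It is nil for the safety set if nobody withdraws before vaccination, and the percentages above rest entirely on assumed counts.

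It would go too far to say that a regimen will be adopted on ELISPOT with its toxicity hidden. The second primary objective asks which regimen gives the highest response; the documents do not say that it will be adopted on that basis alone. Nor does the 2.1-fold dose ratio measure lost safety data. The DSMBplus charter is filed separately and the opening of Section 11.5.1 was not available for this point, so further safety reporting there cannot be excluded. This is a worthwhile and inexpensive correction, not an essential one.

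**What to change.** 1. Align the start date in Section 11.5.5 with Table 3 footnote 22, so that the definition covers the Td booster and cycle-1 TMZ and agrees with its own baseline.
2. Keep the vaccinated set and the vaccine-related endpoint for the primary percentage in Section 15.4.1.
3. Add to Section 15.4.1 a supplementary by-arm table in all randomised patients who start cycle-1 TMZ. It should show Grade 3 or higher events of any attribution; TMZ delays, reductions and discontinuations; and withdrawals before vaccine 1 with reasons. Refer to this set in Section 11.8.
4. Report that table beside the ELISPOT comparison.

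The cost is a wording change and one table, built largely on adverse-event collection and blood counts that Table 3 already schedules. The downside is that Arm 2 may look less favourable than under the vaccinated-only summary. No treatment rule changes.

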11.6 Treatment Period

Patients that have consented onto this study will receive vaccines as indicated above. Once patients have received vaccine therapy, they will be considered as “treated” on this study.

Treatment procedures for the Study Drug Safety Arm are described in Section [11.4.3](#). Further details of potential study drug modification and treatment period pausing criteria is described in Section [15.3](#).

11.7 End of Treatment

One month after final vaccination or once all the blood for immune monitoring has been collected following progression (whichever comes first), the treatment phase of the study will be completed.

11.8 Definition of Evaluable Subjects, On Study, and End of Study

Subjects evaluable for the analysis of the primary endpoints will include all randomized patients who undergo immune monitoring post vaccine #3, prior to 2nd vaccine/TMZ cycle. Survival analyses will include all randomized patients evaluable for the primary outcome.

Safety analyses will include all patients who receive vaccine treatment.

Once the patient signs an ICF, that subject will be considered “on study”. Rationale for taking patient off protocol treatment (see Section 11.10.1 below) will be documented.

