--	---

	
tachycardia, of any duration will be considered an unacceptable toxicity. Although not considered an unacceptable toxicity, any patient with \geq Grade 2 urticaria will not receive further vaccines, will be withdrawn from the study, and will be replaced if less than 3 vaccines have been administered without unacceptable toxicity. The prevalence of unacceptable toxicities occurring during the initial 3 bi-weekly vaccinations or the vaccinations administered concurrently with temozolomide will be continuously monitored. If more than 25% of accrued patients experience unacceptable toxicities, then accrual will be suspended and reported toxicity will be carefully reviewed to determine if modifications to the protocol treatment should occur. Peptide vaccinations employing Montanide ISA-51 as adjuvants have generally been well-tolerated in human patients in numerous phase I-III trials.
 
Treatment Plan: Patients will be vaccinated in conjunction with subsequent 28-day cycles for a total of 6 to 12 adjuvant TMZ cycles after RT if patient is continuing on TMZ (i.e., for patient's who's tumor is methylated or the status is inconclusive). Cycles are every 4 (+ 2) weeks, adjusting for slight delays on startup or scheduling of each 28-day cycle. For patients whose tumor is methylated or the status is inconclusive, the total number of TMZ cycles given will be at the discretion of the treating oncologist. During the 28-day cycles, vaccinations will occur on day 23 (-1 day, + 2 days) of each cycle for each arm: (Arm 1) standard TMZ (200 mg/m²/day on days 1-5 of each 28-day cycle), or (Arm 2) dose-intensified TMZ (100 mg/m²/day on days 1-21 of each 28-day cycle).
 
All vaccines will be given i.d. approximately 10 cm below the inguinal ligament bilaterally. Component A will be administered half in the RIGHT groin and half in the LEFT groin at a maximum of 0.2 mL per intradermal injection. A target of six cycles with maximum of twelve cycles of TMZ may be given to patients enrolled before approval of protocol version 20181218 and to methylated patients enrolled after approval of protocol version 20181218, at the discretion of the treating neuro-oncologist. Unmethylated patients enrolled after approval of protocol version 20181218 will receive only one cycle of TMZ. After the completion of a patient's last TMZ cycle, vaccines will continue every 4-6 weeks for a maximum number of 20 vaccines (unless tumor progression occurs).
 
Patients will be imaged with contrast-enhanced MRI within 2 weeks (+3 days) after vaccine 3 and then approximately every 8 weeks [every 2 cycles thereafter (i.e., end of cycles 3, 5, 7, 9, 11)]. RANO criteria will be used for assessment of pseudo-progression, and patients demonstrating definitive progression will be removed from study. Any patient removed prior to immune monitoring post vaccine 3 will be replaced for immunologic endpoints. Clinical endpoint comparisons will be made amongst patients successfully randomized to adjuvant TMZ treatment arms and receiving at least one vaccine.
 
Blood for immune monitoring will be obtained:
 
• Prior to Td pre-conditioning• During vaccines 1 and 2 (just prior to Component A, 1 and 2 hours after Component A)• Prior to vaccine 3• After vaccine 3 (within 2 weeks of vaccine 3 [+ 3 days])• Prior to vaccines 4 and 6

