Patients who receive more than 1 cycle of TMZ will be vaccinated in conjunction with each **subsequent** 28-day TMZ cycle for a total of 6 to 12 cycles of TMZ after RT followed by further vaccination up to 20 vaccines. Patients who receive only 1 cycle of TMZ will be vaccinated on a 28-day cycle with up to 20 vaccines. All cycles, with or without TMZ, may be given every 4 (+ 2) weeks, in order to adjust for slight delays on startup of each 28-day cycle, and the total number of cycles are given at the discretion of the treating oncologist. During vaccine (+/- TMZ) cycles, vaccinations will occur on day 23 (-1 day, + 2 days) of each cycle for each arm: (Arm 1) standard TMZ (150-200 mg/m²/day on days 1-5 of each 28-day cycle), or (Arm 2) dose-intensified TMZ (75-100 mg/m²/day on days 1-21 of each 28-day cycle). All vaccines will be given i.d. approximately 10 cm below the inguinal ligament bilaterally. A target of six cycles with a maximum of twelve cycles of TMZ may be given to patients enrolled prior to approval of protocol version 20181218 and those with MGMT/inconclusive methylation status if enrolled after approval of protocol version 20181218, at the discretion of the treating neuro-oncologist. After the completion of a patient's TMZ cycles, vaccines will continue to be administered every 4 (+ 2) weeks for a maximum of 20 vaccines (unless tumor progression occurs).

Patients will be imaged with contrast-enhanced MRI after vaccine 3 (at cycle 2 initiation visit) and then approximately every 8 weeks [every 2 cycles thereafter (i.e., end of cycles 3, 5, 7, 9, 11)]. RANO criteria [111] will be used for assessment of pseudoprogression and patients demonstrating definitive progression will be removed from study. Any patient removed prior to immune monitoring post vaccine 3 will be replaced for immunologic endpoints. Clinical endpoint comparisons will be made amongst patients randomized to adjuvant TMZ treatment arms who have received at least one vaccine.

Blood for immune monitoring will be obtained:

- Prior to Td pre-conditioning
- During vaccines 1 and 2 (just prior to Component A, 1 and 2 hours after Component A)
- Prior to vaccine 3
- After vaccine 3 (within 2 weeks of vaccine 3 [+ 3 days])
- Prior to vaccines 4 and 6
- At tumor progression (if feasible)

Patients seen by the Duke neuro-oncology team between these vaccine visits may have blood drawn for immune monitoring at the discretion of the study team.

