15.4.4 Other Exploratory Analyses

Progression-Free Survival and Overall Survival: The Kaplan-Meier estimator will be used to describe the progression-free survival (PFS) and overall survival (OS) experience of patients in each treatment group. These analyses will focus on those patients who have received at least 3 vaccines. PFS is defined as the time between the third vaccine and first documentation of death or disease progression/recurrence. Patients remaining alive without disease progression will have PFS censored at their last follow-up. OS is defined as time between the third vaccine and death. It should be noted that these analyses will focus on only those patients who received Component A alone as we have with other analyses. Additional analyses will describe OS and PFS from randomization.

Radiographic Response: Among the subset of patients with residual disease, the proportion of patients with radiographic response will be estimated with 95% confidence interval.

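### Sections 1/11.1, 11.8 and 15.4.4 give different populations for the survival endpoints, and OS/PFS from randomisation has none of its own; two of the candidate rules would guarantee at least about 50 days of survival

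*Combined protocol and SAP*

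**What the plan says.** Four places in the protocol bear on who enters the survival analyses.

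- Section 1 (Treatment Plan) bases clinical endpoint comparisons on patients "successfully randomized to adjuvant TMZ treatment arms and receiving at least one vaccine". Section 11.1 repeats the rule: "Clinical endpoint comparisons will be made amongst patients randomized to adjuvant TMZ treatment arms who have received at least one vaccine".
- Section 11.8 states: "Survival analyses will include all randomized patients evaluable for the primary outcome". It defines evaluable as randomised with immune monitoring after vaccine 3 and before the second cycle.
- Section 15.4.4, on PFS and OS, states: "These analyses will focus on those patients who have received at least 3 vaccines". It limits the set further to Component A alone and starts both clocks at the third vaccine. It then adds: "Additional analyses will describe OS and PFS from randomization". That sentence names no population. For PFS, "Patients remaining alive without disease progression will have PFS censored at their last follow-up".
- Sections 11.9 and 11.10 deal with follow-up and replacement. Evaluable patients are followed for progression and survival. Randomised patients who leave before the post-vaccine-3 draw are followed for survival only, unless permission is withdrawn (11.10.2). They are replaced, but their data go into all analyses described as appropriate (11.10.3), and those analyses are not named.

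**The concern.** The three sets are nested but different: at least one vaccine; at least three vaccines; three vaccines plus the later draw. Only Section 15.4.4 adds the Component A restriction for survival.

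The choice matters for the output timed from randomisation. A patient can be selected for having reached vaccine 3 only by living that long. If the clock nevertheless starts at randomisation, the interval up to vaccine 3 contains no deaths by construction, and the patients who died or withdrew in it are missing. The estimated survival curve is then too high at the start.

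Reaching vaccine 3 is also a post-randomisation event. Section 11.10.1 lists TMZ intolerance, clinical decline and progression among the withdrawal reasons, so the selection could differ between two arms that differ in their TMZ regimen. The documents give no basis for saying in which direction.

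An analyst could therefore produce the same planned output for all randomised patients or for a selected group, depending on which sentence is followed.

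**Working it through.** **1. Check of the schedule against the plan's own figure.** Count TMZ day 1 of cycle 1 as day 1. Td is given on day 22 (+1) and vaccine 1 the next day (11.4.2), so vaccine 1 falls on day 23. Vaccines 2 and 3 follow at 14-day (+3) intervals (Sections 1 and 11.1).

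- Vaccine 2: 23 + 14 = day 37. Vaccine 3: 37 + 14 = day 51.
- Earliest TMZ cycle 2: 51 + 14 = day 65. An undelayed cycle 2 would start on day 29, so the delay is 65 − 29 = 36 days, or 35 if vaccine 1 is on day 22.

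This reproduces the stated delay of at least about 35 days.

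**2. Guaranteed survival from TMZ day 1.** Randomisation is the date the TMZ regimen is assigned (Section 6) and TMZ starts after it, so time from randomisation is at least this long.

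| Rule applied to the from-randomisation output | Guaranteed time |
|---|---|
| All randomised | 0 days |
| At least one vaccine (1, 11.1) | 23 − 1 = 22 days |
| At least three vaccines (15.4.4) | 51 − 1 = 50 days (49 with the −1 day window in Section 1) |
| Post-vaccine-3 draw (11.8) | more than 50; nominally 50 + 14 = 64 days |

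The 64 days assume that the draw is 2 weeks after vaccine 3, as in Table 3 footnote 15. Sections 1 and 11.1 place it within 2 weeks, so 64 is not a floor.

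**3. Illustrative size for OS.** The documents give no survival distribution from randomisation, so this step rests on assumptions.

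- Median: Section 9 puts survival below 15 months, from diagnosis in Section 9.1. From that subtract 3 to 5 weeks from surgery to RT (assumed), 6 weeks of RT (from the earlier trial in Section 9.7) and 2 to 6 weeks to TMZ (Table 3 footnote 7). The sum is 11 to 17 weeks, about 2.5 to 3.9 months, leaving about 11 to 12.5 months. The range used is 11 to 15.
- Model: Weibull with median M and shape k. Given survival to L, the median is M × (1 + (L/M)^k)^(1/k). The share dying before L is 1 − 0.5^((L/M)^k).
- L = 50 days / 30.44 = 1.64 months.

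| M (months) | k = 1 (constant hazard): shift, share omitted | k = 1.5 | k = 2 |
|---|---|---|---|
| 11 | 1.64 months, 9.8% | 0.42, 3.9% | 0.12, 1.5% |
| 15 | 1.64 months, 7.3% | 0.36, 2.5% | 0.09, 0.8% |

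With L = 64 days (2.10 months), the shifts are 0.15 to 0.60 months for k = 2 to 1.5, and 2.10 months for k = 1. A shape below 1 would give a larger shift than k = 1, so the constant-hazard figure is not a strict upper bound. The model selects on survival only. It does not capture patients withdrawn alive before vaccine 3.

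**4. Scale.** With 13 per arm, exponential survival and all deaths observed, the 95% confidence interval for a median of 11 months is 11 × exp(±1.96/√13), or 6.4 to 18.9 months.

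**5. PFS.** No shift is calculated. Progression is dated by surgical or, failing that, radiographic confirmation (Section 6). The first on-treatment MRI comes after vaccine 3 (1, 11.1, 12.8), and stable patients with changes consistent with pseudoprogression continue (11.3). Few progressions would be dated before vaccine 3 in any population, so a continuous-time model would not describe the observed PFS.

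**The case against.** The strongest reply is that this is a narrow wording matter. Section 15.4.4 is the specific statistical section. For its main analysis it gives a population, a time origin and a censoring rule, and these are mutually consistent. Sections 11.8 and 15.4.4 nearly coincide, differing by one draw due about two weeks later. The one-vaccine rule concerns comparisons, whereas the stated objective is only to describe PFS and OS. Sections 11.10.2 and 11.10.3 can be read as already placing every randomised patient in the additional analysis, and the survival data for that are to be collected.

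Most of this stands. It confines the problem to one sentence about additional, exploratory analyses. It does not settle which population that sentence uses. If the paragraph's three-vaccine focus carries over, the ambiguity goes but the 50 guaranteed days become certain. If Section 11.8 governs, the guaranteed time is longer. Only the all-randomised reading avoids the problem, and the plan never states it.

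Three stronger readings are tempting but not supported. A reader might infer that the plan's main survival analysis is biased by guaranteed time. As 15.4.4 writes it, the clock and the selection both start at vaccine 3, so it is not. A reader might infer that a biased from-randomisation analysis is definitely planned. The passages conflict, and some point to including everyone. A reader might take the 8 evaluable of 15 Component-A-only patients in Section 15.1 as an exclusion rate. It is a snapshot on 20200110, and some of the other 7 may not yet have reached the draw.

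**Conclusion.** The inconsistency is real and its severity is minor. Three populations are stated without an order of precedence, and OS/PFS from randomisation has none of its own. Applying Section 11.8 or the three-vaccine focus to that output would guarantee at least about 50 days of survival (49 with the −1 day window, nominally about 64 at the draw) and leave out early deaths and withdrawals. The one-vaccine rule would guarantee about 22 days. These day counts follow from the protocol's schedule.

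The effect on median OS depends on the assumed medians and hazard shapes: about 0.1 to 0.4 months under a rising hazard and 1.6 months under a constant hazard, for 50 days. Either is small beside the sampling error with 13 per arm. No figure should be attached to PFS. The primary safety and ELISPOT analyses are not affected.

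**What to change.** 1. In Section 15.4.4, state that OS and PFS from randomisation include all randomised patients in the Component-A-only period, whatever number of vaccines they received. Define that period by a randomisation date or protocol-version cut-off applied equally to both arms.
2. Deal openly with the first four patients after randomisation resumed (Section 15.1). Both standard-TMZ patients received Component B. Both dose-intensified patients had it dropped before treatment. If the latter two are included, disclose that their two concurrent standard-TMZ patients are not, and show the result with and without them.
3. Keep the third-vaccine analysis in patients with at least three vaccines and label it a landmark analysis.
4. Align the population sentences in Sections 1, 11.1 and 11.8, and name in 11.10.3 the analyses that include replaced patients.
5. In 11.9 and 11.10.2, record progression for early withdrawals where routine care provides it and consent allows. Otherwise state that their PFS is censored, and limit the all-randomised conclusion to OS.

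The cost is wording in a few sections, a little data abstraction, and possibly less favourable exploratory medians.
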